3.2 Secondary Objective(s)

- 3.2.1 To detect tumor or lymph node by MSOT before and after surgical removal
- 3.2.2 To determine tumor positivity based on tissue pathology and detection of oxy- and deoxy-hemoglobin using MSOT localization
- 3.2.3 To determine tumor volume by MSOT before and after surgical resection

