4.0 Patient Selection

4.1 Inclusion Criteria

- 4.1.1 Patients with an identified solid tumor, i.e. breast (Stage I-IV), melanoma (Stage I-IV), HNSCC (Stage I-III), pancreatic (Stage I-III), ovarian (Stage I-IV) that is scheduled for surgical removal of the tumor and completed standard imaging prior to surgery
- 4.1.2 Have acceptable hematologic status [total hemoglobin (tHb) \geq 10 mg/dL]
- 4.1.3 Patients \geq 18 yrs of age
- 4.1.4 Patient provided a signed and dated informed consent
- 4.1.5 Willing to comply with study procedures and be available for the duration of the study
- 4.1.6 Ability to understand and the willingness to sign an IRB-approved informed consent document.

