7.0 Study Plan

7.1 Study-Related Activities

Study Procedures

- Upon receipt of a signed consent form, the research study team will generate a unique identification number so that subjects are de-identified for analysis of data. *Any standard imaging measurements will be added in [Appendix A and B](#).* This unique identification number will be used on the case report form ([Appendix A and B](#)).
- Patients will go through standard care procedures to prepare for surgery. Medically established diagnostic procedures will be used to detect tumor and lymph node margins.
- To evaluate the safety of MSOT ([Figure 2](#)), the device will be used to obtain images of the tumor or lymph node margins for investigational use only to compare to clinical pathology and patient's medical record.
- As part of the standard of care surgery preparation for cancer resection for all tumor types, patients will be injected with standard doses of Isosulfan Blue/ Indocyanine (IC) Green for either lymph node or tumor identification as part of the standard surgical procedure. The MSOT device will detect the presence of dye at the standard dose of dye used for surgical evaluation of tissue.

Figure 2 The MSOT Acuity

- Images will be obtained pre- and post-surgery (example simulation of operating room shown [Figure 3](#)). All imaging will be done in a closed surgical patient; no imaging will be performed on an open surgical patient. [name] has been trained in the use of the MSOT Acuity by the manufacturer, and she will be the MSOT operator for all MSOT imaging for this study. [name] will train the surgeon and surgical staff in the proper procedure for using the handheld

[figure not shown]
[figure not shown]
[figure not shown]
[figure not shown]
[figure not shown]
Figure 3: Demonstration of MSOT scanning procedure. A. Handheld detector covered with drape; B. surgeon; C. MSOT Acuity; D. trained MSOT operator.

detector and will maintain training records for this purpose. Only [name] and her research staff will perform post-imaging analysis on the de-identified digital images stored on the MSOT Acuity. The pathologist and clinician will perform all clinical evaluations of tumor samples as well as post-imaging assessment of treatment area and report where indicated on the imaging case report form. MSOT imaging will be for research only and no treatment decisions will be based on the MSOT images obtained.

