24	Once the surgeon has the probe in place, the MSOT operator will press the foot pedal to activate the laser radiation for imaging. The MSOT operator will communicate with the surgeon as an image is acquired and coordinate the timing of the laser activation for additional scans. Release of the foot pedal will immediately shut down the laser system and stop the imaging procedure.
25	
The MSOT operator will record Scan comments on the screen to be saved for each image acquired in the image sequence.
 
NOTE: Total number of images acquired in the image sequence will be recorded on the Imaging Case Report Form (Appendix A).

26	
A yellow indicator in the signaling device on top of the system and in the front panel shows that laser light is emitted through the aperture of the handheld probe. Keep the aperture of the probe on the region of interest or towards the floor. NEVER direct the aperture of the probe towards eyes while this indicator is on. Once the foot pedal is released laser emission is stopped and the laser emission indicator will turn off.
	
27	The patient will undergo surgery for resection of the identified volume of tissue according to standard care.	
28	After tumor or lymph node removal and incision has been closed, the area of interest will be reimaged by MSOT to obtain post-surgery images in the operating room by repeating steps 16 through 23.	
29	An estimate of the percent amount of tumor remaining will be estimated by algorithms within in the MSOT computer programming for investigational use only.	
30	The resected tumor will be taken to Pathology for volume assessment and pathological identification per medically established diagnostic standard care.	
31	Data from the MSOT imaging is for research purposes only and not for treatment, and digital images will be kept on the MSOT computer, which will be stored in a secured room accessible only to study personnel.	
32	Key parameters will be recorded on (Appendix A and B).	

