For binary outcomes (positivity and presence of dye), we will estimate the MSOT approach and the corresponding 95% Clopper-Pearson exact binomial confidence interval. Accuracy is defined as the number of patients where the MSOT and standard of care approach are in agreement (i.e., both are positive or both are negative). In addition, we can examine other characteristics of the two approaches including sensitivity, specificity, positive predictive value and negative predictive values.

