Appendix A – Imaging and Tissue Data Collection Form

Study Number: OU-SCC-MSOT PID: 0 1 - _____

Investigator: [name] Surgery Date: ____/____/____

1) Tumor or Lymph Node Assessments:

a) Target tissue

Tumor

Lymph Node

b) Standard of care method of imaging

MRI _____ tumor amount

PET _____ tumor amount

CT _____ tumor amount

Other: _____ tumor amount

c) Did patient receive neoadjuvant therapy?

Yes

No

d) MSOT Image acquired?

Yes

No

e) Was an indicator dye used during surgery?

Yes

[figure not shown]
No

f) If an indicator dye used during surgery, please indicate which dye.

Isosulfan Blue IC Green

2) Location of Imaging

a) Please circle the location of the imaging (below) and provide further description as necessary

[https://anatomyclass123.com /](https://anatomyclass123.com/)

b) Erythema post-MSOT Imaging (RTOG)

i. Time after imaging: (hr: min) _____

ii. Grade (RTOG)

- 0 No erythema present
- 1 Follicular, faint or dull erythema, epilation, dry desquamation, decreased sweating
- 2 Tender or bright erythema, patchy moist desquamation, moderate edema
- 3 Confluent, moist desquamations other than skin folds, pitting, edema
- 4 Ulceration, hemorrhage, necrosis

3) Clinical Pathology Assessment

a) Date or diagnosis (month / year):

b) Positive tumor tissue:

Yes No
 c) For Pancreatic melanoma breast HNSCC ovarian (check one) indicate stage at diagnosis (**TNM classification**):

Tx T0 Tis T1 T2 T3 T4
 Nx N0 N1 N2 N3
 Mx M0 M1

d) Tumor subtype (if applicable) _____

4) Skin temperatures

Pre-Surgery MSOT imaging			
Pre-imaging Skin Temperature (°C)		Time	
Post-imaging Skin Temperature (°C)		Time	

Post-Surgery MSOT imaging			
Pre-imaging Skin Temperature (°C)		Time	
Post-imaging Skin Temperature (°C)		Time	

5) Patient Monitoring (*)please note that patients must be monitored daily for adverse events until discharge). Please answer yes or no if Erythema at grade III or higher or change in skin pigmentation occurs.**

Yes No

_____ Post surgery	_____ 8 day
_____ 1 day	_____ 9 day
_____ 2 day	_____ 10 day
_____ 3 day	_____ 11 day
_____ 4 day	_____ 12 day
_____ 5 day	_____ 13 day
_____ 6 day	_____ 14 day
_____ 7 day	_____ 15 day

Discharge date: _____

6) Adverse event. Please answer yes or no if Erythema at grade III or higher or change in skin pigmentation occurs.

Yes No

If yes, please fill out details below:

_____ Erythema _____ Time _____ Date

_____ Changes in skin pigmentation _____ Date

7) MSOT Scan Times:

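### For lymph-node targets the pathology reference is not tied to the tissue imaged, and tumor and node results are not kept apart

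*Protocol*

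**What the plan says.** Nodes are an intended target throughout.

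- Protocol 3.2.1 sets the objective "To detect tumor or lymph node by MSOT before and after surgical removal".
- Protocol 7.1 uses the device to "obtain images of the tumor or lymph node margins for investigational use only to compare to clinical pathology" and the medical record.
- Table 2, step 28: "After tumor or lymph node removal and incision has been closed, the area of interest will be reimaged by MSOT".
- Appendix A item 1a offers tumor and lymph node as the target tissue.

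The pathology side is narrower.

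- Two steps later, step 30 reads "The resected tumor will be taken to Pathology for volume assessment and pathological identification per medically established diagnostic standard care". No node is mentioned.
- Table 2, step 2 provides one case report form per participant. Its only post-resection pathology result is Appendix A item 3b, labelled "Positive tumor tissue", yes or no, with no link to item 1a.
- Item 3c records T, N and M, but as stage at diagnosis.

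The analysis sections do not close the gap. Protocol 10.2 takes the reference from pathology reports after resection and says "Accuracy is defined as the number of patients where the MSOT and standard of care approach are in agreement". It makes no split by target. SAP 7.c compares tumor positivity from pathology with MSOT and does not mention target tissue.

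**The concern.** An accuracy figure means something only if each reading is judged against the tissue that was read. Under Protocol 4.1.1 every patient has an identified solid tumor and is "scheduled for surgical removal of the tumor and completed standard imaging prior to surgery". The primary will therefore be positive in nearly everyone, whereas a node may or may not be. If the one recorded yes/no describes the primary, node readings are judged against the wrong specimen: true negatives become errors and false positives become successes. Protocol 10.2 also proposes specificity and negative predictive value. Specificity needs reference-negative patients, and there would be almost none; negative predictive value would be close to zero however good the reader. Where both tumor and node are imaged in one patient, which outcome 6.2.3 allows, item 3b cannot hold both results.

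**Working it through.** **1. Two readings of item 3b.** The documents allow both.

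- *Reading A, primary tumor.* Step 30 names only the tumor, and item 3b sits between date of diagnosis and stage at diagnosis.
- *Reading B, tumor found in the imaged tissue.* Item 1a has already set the target.

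For a patient with a positive primary and a negative node, with the node imaged, A gives yes and B gives no. The completed form does not show which was used.

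**2. Inputs.** From Protocol 10.3: N = 50 scanned, or 45 if stopped early. The documents give no accuracy figure, node-target count or node positivity, so there is no plan figure to reproduce for this point. Assumed: m = 10 to 20 node targets, node positivity q = 20 to 50%, one target per patient, all primaries positive.

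**3. Check of the interval method.** Exact Clopper-Pearson upper limits are 7.11% for 0/50 and 19.23% for 4/50. For 0, 1, 2 and 3 of 45 they are 7.87%, 11.77%, 15.15% and 18.27%. Protocol 10.3 gives 7.1%, below 20%, and 7.9%, 11.7%, 15.1%, 18.3%. These agree within 0.1 point.

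**4. Reading A, perfect reader.** Every negative node is scored as a disagreement, so agreements = N − m(1 − q).

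| m | q | Agreements (N = 50) | Scored accuracy | Exact 95% CI |
|---|---|---|---|---|
| 10 | 50% | 50 − 5 = 45 | 90% | 78.2–96.7% |
| 10 | 20% | 50 − 8 = 42 | 84% | 70.9–92.8% |
| 20 | 50% | 50 − 10 = 40 | 80% | 66.3–90.0% |
| 20 | 20% | 50 − 16 = 34 | 68% | 53.3–80.5% |

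True accuracy is 50/50 in every row, and there are no reference negatives, so specificity cannot be computed. With N = 45 the range is 29/45 = 64.4% to 40/45 = 88.9%. Conversely, a reader who calls every node positive is scored as fully correct on nodes.

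**5. Reading A, imperfect reader.** Assume sensitivity and specificity of 80%, so true accuracy is 80%. Scored accuracy = [0.8(N − m) + 0.8mq + 0.2m(1 − q)]/N.

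- m = 10: (32 + 1.6 + 1.6)/50 = 70.4% at q = 20%; (32 + 4 + 1)/50 = 74.0% at q = 50%.
- m = 20: (24 + 3.2 + 3.2)/50 = 60.8% at q = 20%; (24 + 8 + 2)/50 = 68.0% at q = 50%.

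**6. Reading B.** The reference is right, but target types are still pooled. All reference negatives are nodes: 5 to 8 when m = 10, and 10 to 16 when m = 20. Reference positives are mostly primaries: 40 of 42 to 45 when m = 10, and 30 of 34 to 40 when m = 20. Pooled specificity would describe nodes and pooled sensitivity mainly tumors. As an example, tumor accuracy of 100% and node accuracy of 50% with m = 10 give (40 + 5)/50 = 90%, which hides the node result.

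**The case against.** A reader might infer that the plan scores node readings against the primary tumor. It does not say so. Protocol 10.2.1 takes the reference from post-resection pathology reports, 7.1 compares tumor or node images with clinical pathology and the medical record, and 7.2 allows six months of record review to gather pathology. Node histology could come from any of these.

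A reader might also infer that no node result can reach the study data. That is not shown: Protocol 9.2.2 has the team develop a REDCap database and study-specific forms, and does not say that Appendices A and B are the whole dataset. Reading B of item 3b is reasonable, and a field that is nearly always yes would be of little use, which counts against Reading A. Primaries need not all be positive, since item 1c anticipates neoadjuvant therapy.

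Dye identification (6.2.3), the outcome that names nodes, is a separate binary measure with its own tissue field in Appendix B. So the plan does not merge everything into one figure; the pooling of targets occurs within each outcome. The documents also define no malignant/benign MSOT call for a node, which the illustration presupposes.

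All of this stands, and it makes the point conditional. It does not settle which specimen is the reference for an imaged node, give item 3b room for two results, or separate target types in the analysis.

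**Conclusion.** The concern holds as a gap with a specific consequence. For lymph-node targets the reference specimen is not tied to what was imaged, and tumor and node results are not separated. If item 3b is completed for the primary, a perfect reader could be scored 68 to 90% accurate in 50 patients. That range rests wholly on the assumed 10 to 20 node targets and 20 to 50% node positivity; it illustrates the direction and possible size and does not predict the result. If 3b is completed for the imaged tissue, the score is correct but pooled, and one field cannot serve a patient with both targets. The primary safety analysis, the expansion decision and early stopping rest on adverse events and are untouched. The change is worth making because it bears on a named objective and costs little.

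**What to change.** - Table 2, step 30: name resected lymph nodes as well as the resected tumor.
- Appendix A: replace item 3b with a post-resection pathology result for each imaged target, tumor and node on separate lines. Abstract these from routine pathology reports, retrospectively if scanning is complete. This assumes that those reports cover the removed nodes.
- Protocol 10.2 and SAP 7.c: pair each MSOT reading with the pathology of the same target, and report tumor and node accuracy separately, each with an exact Clopper-Pearson interval. The pairing needs an MSOT positivity call for each target; Appendix B has dye yes/no fields but none for tumor positivity.

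The cost is a few form fields, a few sentences and smaller denominators. With no disagreements the lower exact limit is 0.025^(1/n): 92.9% for n = 50, against 91.2% for 40 tumors and 69.2% for 10 nodes, or 88.4% for 30 tumors and 83.2% for 20 nodes. The wider node interval reflects how little the study can say about nodes, which pooling would conceal.

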7.2 Duration of Follow Up

Subjects will be actively enrolled only for the duration of pre-op through surgical recovery, and until post-op discharge unless any study-related adverse event occurs. Medical record review will occur up to 6 months to allow for follow-up pathology assessments to be gathered and provide information to allow for analyses to be performed as previously described.

7.3 Criteria for Removal from Study

Patients can request to withdraw from the study at any time. Should patients consent to the study, but have tumor progression that prevents them from being a surgical candidate within 30 days, these patients may be removed at the Investigator's discretion. There is no reason to remove a patient otherwise from the study.

8.0 Adverse Events List and Reporting Requirements

An adverse event (AE) is any untoward medical occurrence in a patient or clinical investigation subject administered an investigational product, and which does not necessarily have to have a causal relationship with this treatment. An AE can therefore be any unfavorable and unintended sign (including an abnormal laboratory finding, for example), symptom, or disease temporally associated with the use of a medical product, whether or not considered related to the medical product. All AEs are assessed by the center for severity, causality, outcome, seriousness, and if unanticipated.

8.1 Adverse Event List for MSOT

A slight, reversible reddening and temperature increase of sensitive skin. All adverse events and expected treatment effects, including mild events, will be monitored throughout the study until discharge.

8.2 Adverse Event Characteristics

- **CTCAE term (AE description) and grade:** The descriptions and grading scales found in the revised NCI Common Terminology Criteria for Adverse Events (CTCAE) version 5.0 will be utilized for AE reporting. All appropriate treatment areas should have access to a copy of the CTCAE version 5.0. A copy of the CTCAE version 5.0 can be downloaded from the CTEP web site (<http://ctep.cancer.gov>).
- **'Expectedness':** AEs can be 'Unexpected' or 'Expected' (see Section 8.1 above) for expedited reporting purposes only.
- **Attribution** of the AE:
 - Definite – The AE **is clearly related** to the study treatment.
 - Probable – The AE **is likely related** to the study treatment.
 - Possible – The AE **may be related** to the study treatment.
 - Unlikely – The AE **is doubtfully related** to the study treatment.
 - Unrelated – The AE **is clearly NOT related** to the study treatment.

8.3 Serious Adverse Events (SAE)

Serious is defined as an adverse event that results in the following outcome:

- Death
- Life-threatening event (i.e. an event that places the patient, in the view of the investigator, at immediate risk of death from the event as it occurred). This does not include an event that, had it occurred in a more severe form, might have caused death

- Requires or prolongs hospitalization
- Results in persistent or significant disability/incapacity
- Congenital anomaly/birth defect.
- Important medical event that, based upon appropriate medical judgement, may jeopardize the patient, and may require medical or surgical intervention to prevent one of the outcomes listed above.

8.4 Unanticipated Adverse Device Effects Reporting Requirements

Unanticipated Adverse Device Effect (UADE) means any serious adverse effect on health or safety or any life-threatening problem or death caused by, or associated with, a device, if that effect, problem, or death was not previously identified in nature, severity, or degree of incidence in the investigational plan or application (including a supplementary plan or application), or any other unanticipated serious problem associated with a device that relates to the rights, safety, or welfare of subjects.

A medical review shall immediately occur with all reported Unanticipated Adverse Device Effects (UADE). The UADE shall be assessed for an unreasonable risks' determination. If an unreasonable risk has been determined, then the trial or the parts that cause the risk shall be stopped between 5-15 working days after making the determination.

8.5 Reporting of Unanticipated Problems, Adverse Events or Deviations

Any unanticipated problems, serious and unexpected adverse events, deviations or protocol changes will be promptly reported by the principal investigator to the IRB and sponsor or appropriate government agency, if appropriate and per institutional guidelines.

A description of all AEs and UADEs will be recorded on REDCap. All UADEs should be reported using the Sponsor Form (UADE Reporting Form) and MedWatch3500A to the following email or fax within 24 hours of the site notification of the event:

Email: [contact] or
[contact]

In compliance with FDA regulations 21 CFR 812.150, any UADEs occurring during the investigation should be reported to the sponsor and reviewing IRB within 10 days of first notice of the event. The sponsor will conduct an

evaluation of the UADE and report the results of such evaluation as an UADE Report to FDA, all reviewing IRBs, and participating investigators within 10 working days after the sponsor first receives notice of the effect.

An UADE Report will consist of a completed MedWatch 3500A form and a cover letter that provides an analysis of the event. Thereafter the sponsor shall submit such additional reports concerning the effect as per requests from FDA.

8.6 Post-imaging Procedural Events for MSOT

The post-imaging procedural events for MSOT are those events that are expected and standard to post-imaging as for ultrasound and include slight, reversible reddening and temperature increase of sensitive skin for a duration of ≤ 24 hours post-surgery. All unexpected events shall be captured. Post-imaging procedural events that occur in increased frequency and severity over what should normally occur in the medical opinion of the investigator will be considered adverse events (AE). AEs will be reported.

9.0 Data and Safety Monitoring

Safety oversight will be performed by Stephenson Cancer Center's (SCC) internal Data and Safety Monitoring Committee (DSMC). The DSMC is composed of individuals with the appropriate expertise in adult and pediatric hematology and medical oncology, radiation oncology, translational and correlative science, pharmacy, nursing and biostatistics. The DSMC operates under the rules of an approved data safety monitoring plan which complies with the National Cancer Institute (NCI) guidelines published as *Essential Elements of a Data and Safety Monitoring Plan for Clinical Trials Funded by NCI* as of January 2005 and the "NIH Policy for Data and Safety Monitoring," *NIH Guide for Grants and Contracts*, <http://grants.nih.gov/grants/guide/notice-files/not98-084.html>.

The Data Safety Monitoring Committee is charged with oversight of participant safety, study conduct and the validity and integrity of data for clinical trials at SCC. While the focus of the DSMC is to monitor interventional investigator-initiated trials (IITs) that are not subject to external monitoring, it has the authority to monitor any SCC protocol when potential concerns are identified. The DSMC also has the authority to suspend or close a study until the principal investigator addresses any issues that may cause harm or increase risks to subjects. The DSMC reports all findings to the Institutional Review Board (IRB).

Under the direction of the DSMC chair, a full board meeting is convened on a quarterly basis to review the accumulated safety data, accrual information, and additional information as stated in the DSMC plan.

